**Non-Target Lesions (NTLs) and new lesions – site investigator data**

At each visit, the investigator should record an overall assessment of the NTL response. This section provides the definitions of the criteria used to determine and record overall response for NTL at the investigational site at each visit.

NTL response will be derived based on the Investigator’s overall assessment of NTLs as described in [Table 8](#).

**Table 8: NTL visit responses**

Visit Responses	Description
Complete Response (CR)	Disappearance of all NTLs present at baseline with all lymph nodes non-pathological in size (<10 mm short axis).
Progressive Disease (PD)	Unequivocal progression of existing NTLs. Unequivocal progression may be due to an important progression in one lesion only or in several lesions. In all cases the progression MUST be clinically significant for the physician to consider changing (or stopping) therapy.
Visit Responses	Description
Non-CR/Non-PD	Persistence of one or more NTLs with no evidence of progression.
Not Evaluable (NE)	Only relevant when one or some of the NTLs were not assessed and, in the investigator's opinion, they are not able to provide an evaluable overall NTL assessment at this visit. Note: For participants without TLs at baseline, this is relevant if any of the NTLs were not assessed at this visit and the progression criteria have not been met.
Not Applicable (NA)	Only relevant if there are no NTLs at baseline.

CR = complete response; NA = not applicable; NE = not evaluable; NTL = non-target lesion; PD = progressive disease.

To achieve ‘unequivocal progression’ on the basis of NTLs, there must be an overall level of substantial worsening in non-target disease such that, even in the presence of SD or PR in TLs, the overall tumour burden has increased sufficiently to merit a determination of disease progression. A modest ‘increase’ in the size of one or more NTLs is usually not sufficient to qualify for unequivocal progression status.

Details of any new lesions will also be recorded with the date of assessment. The presence of one or more new lesions is assessed as progression.

A lesion identified at a follow up assessment in an anatomical location that was not scanned at baseline is considered a new lesion and will indicate disease progression.

The finding of a new lesion should be unequivocal: i.e. not attributable to differences in scanning technique, change in imaging modality or findings thought to represent something other than tumour.

New lesions will be identified via a Yes/No tick box. The absence and presence of new lesions at each visit should be listed alongside the TL and NTL visit responses.

A new lesion indicates progression so the overall visit response will be PD irrespective of the TL and NTL response.

If the question ‘Any new lesions since baseline’ has not been answered with Yes or No and the new lesion details are blank this is not evidence that no new lesions are present but should not overtly affect the derivation. This scenario (i.e. whereby new lesion response is NE), should only occur in exceptional cases, as missing data for the new lesion field should always be queried.

Symptomatic progression is not a descriptor for progression of NTLs: it is a reason for stopping study therapy and will not be included in any assessment of NTLs.

Participants with ‘symptomatic progression’ requiring discontinuation of treatment without objective evidence of disease progression at that time should continue to undergo tumour assessments where possible until objective disease progression is observed.

#### 4.9.2 Overall visit RECIST 1.1 response

The previously defined TL and NTL visit responses will be combined with new lesion information to give an overall visit response (see [Table 9](#)).

**Table 9: Overall visit responses**

TARGET	NON-TARGET	NEW LESIONS	OVERALL VISIT RESPONSE
CR	CR or NA	No (or NE)	CR
CR	Non-CR/Non-PD or NE	No (or NE)	PR
PR	Non-PD or NE or NA	No (or NE)	PR
SD	Non-PD or NE or NA	No (or NE)	SD
PD	Any	Any	PD
Any	PD	Any	PD
Any	Any	Yes	PD
NE	Non-PD or NE or NA	No (or NE)	NE
NA	CR	No (or NE)	CR
NA	Non-CR/Non-PD	No (or NE)	SD

TARGET	NON-TARGET	NEW LESIONS	OVERALL VISIT RESPONSE
NA	NE	No (or NE)	NE

***Blinded Independent Central Review of Tumour Response***

Blinded independent central review (BICR) assessment may be introduced if the cohort is expanded, subject to an approved protocol amendment.

**4.9.3 Best Objective Response by RECIST 1.1**

Best objective response (BoR) is calculated based on the overall visit responses from each RECIST assessment. It is the best response a participant has had following first dose, prior to starting any subsequent cancer therapy or up to and including RECIST progression or the last evaluable assessment in the absence of RECIST progression. Categorisation of BoR will be based on RECIST using the following response categories: CR, PR, SD, PD and NE.

The confirmation of CR or PR should be performed at the next scheduled RECIST assessment and must not be less than 4 weeks later. For determination of a best response of SD, the earliest of the dates contributing towards an overall visit assessment will be used. SD should be recorded at least 8 weeks minus 1 week (to allow for an early assessment within the assessment window), after first dose/administration of study intervention. For CR/PR, the initial overall visit assessment which showed a response will use the latest of the dates contributing towards an overall visit assessment.

For participants who die with no evaluable RECIST assessments post-baseline, if the death occurs ≤17 weeks (i.e., 16 weeks + 1 week to allow for a late assessment within the assessment window) after first dose/administration of study medication, then BoR will be assigned to the progression (PD) category. For participants who die with no evaluable RECIST assessments, if the death occurs >17 weeks after start of treatment then BoR will be assigned to the NE category.

However, if the participant progresses or dies after two or more missed visits, the participant will be censored at the time of the latest evaluable RECIST 1.1 assessment prior to the two missed visits. NE is not considered a missed visit.

For participants whose progression event is death, BoR will be calculated based upon all evaluable RECIST assessments prior to death.

**4.9.4 Bone progression using PCWG3 visit responses**

For modules requiring PCWG3 results, the PCWG3 criteria will be used to determine each participant’s visit response. It will also be used to determine if and when a participant has progressed.

***Evaluation of Bone progression status***

Bone lesions will be assessed by bone scan and will not be part of the RECIST v1.1 malignant soft tissue assessment. Bone lesions identified on a whole-body isotopic bone scan at baseline should be recorded and followed by the same method as per baseline assessment.

In this study isotopic bone scans will be used as a method of assessment to identify the presence of new bone lesions at post-baseline follow-up visits regardless of scheduled or unscheduled. New lesions will be recorded where a positive and unequivocal hot-spot that was not present on the baseline scan assessment is identified on a bone scan performed at any time during the study. The investigator should consider the positive hot-spot to be a significant new site of malignant disease and represent true disease progression in order to record the new lesion.

Baseline radiological tumour assessments are to be performed no more than 28 days before the first dose/administration of study medication and ideally as close as possible to the start of study treatment. Tumour assessments are then performed every 8 weeks ( $\pm 1$  week) following Cycle 1 Day 1 of the study treatment up to 1 year, then every 12 weeks ( $\pm 1$  week) until radiographic disease progression as defined by RECIST 1.1. (soft tissue; refer to [section 4.9.1](#)) and PCWG3 (bone).

If an unscheduled assessment was performed and the participant has not progressed, every attempt should be made to perform the subsequent assessments at their originally scheduled visits. This schedule is to be followed in order to minimise any unintentional bias caused by some participants being assessed at a different frequency than other participants.

All bone lesions (or sites of disease) should be identified at baseline. Their status should be followed at subsequent visits. At each visit an overall assessment of the bone lesion progression should be recorded by the investigator.

Progression on a bone scan is identified using PCWG3 as follows:

- At 8 weeks scan:  
2 or more new metastatic bone lesions are observed on the first 8-week scan compared to the baseline assessment. The confirmatory scan, performed at least 6 weeks later and preferably no later than the next scheduled visit for a bone scan (i.e., Week 16), must show 2 or more additional new metastatic bone lesions (for a total of 4 or more new metastatic bone lesions since the baseline assessment) for progression to be documented.  
Note – the first bone scan completed after baseline will be considered the ‘8-week scan’ regardless if taken at week 8 or at an unscheduled assessment.
- After the 8 week scan:  
2 or more new metastatic bone lesions are observed compared to the 8 week assessment. The confirmatory scan, performed at least 6 weeks later and preferably at the next scheduled visit for a bone scan, must show the persistence of or an increase in the number of metastatic bone lesions compared to the prior scan for progression to be documented.

The date of progression is the date of the scan that first documents the second new lesion.

[Table 10](#) provides the definitions for bone progression at each visit for bone lesions.

### **Table 10: Bone Progression Status**

Visit Responses	Description
Non-Progressive Disease (Non-PD)	No evidence of progression, or appearance of one new bone lesion, or non-fulfilment of the progression criteria including new lesions without confirmation of progressions.
Progressive Disease (PD)	Bone lesions fulfilling requirements for at least 2 new lesions and confirmation of progression.
Not Evaluable (NE)	Only relevant if a follow-up scan is not performed.

#### 4.9.5 Best Overall radiological objective response

##### *Overall radiological objective response*

The visits responses for soft tissue (according to RECIST 1.1 criteria) and bone progression status (according PCWG3 criteria), and how they are combined to give an overall radiological objective visit response is given in [Table 11](#).

**Table 11: Overall Radiological Visit Response**

Overall visit soft tissue response (RECIST 1.1)	Bone progression status (PCWG3)	Bone lesions at visit Present/Absent	Overall radiological visit response
CR	Non-PD	Absent	CR
CR	Non-PD	Present	PR
CR	NE	-	PR
PR	Non-PD or NE	Any	PR
SD	Non-PD or NE	Any	SD
NED	Non-PD or NE	Any	Non-PD
NE	Non-PD or NE	Any	PD
PD	Any	Any	PD
Any	PD	Any	PD

CR = complete response; NE = not evaluable (only relevant if a follow-up bone scan is not performed); NED = no evidence of disease (only relevant where there is no TL and NTL from baseline); PD = progressive disease; PR = partial response; SD = stable disease.

Confirmation of response (CR or PR) should be performed at the next scheduled RECIST and PCWG3 assessment (and must not be less than 4 weeks later) following the date the criteria for response were first met (see [Table 12](#)).

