### 4.9.1 Response using RECIST 1.1.

For modules requiring RECIST results, the RECIST tumour response data will be used to determine each participant’s visit response according to RECIST version 1.1. It will also be used to determine if and when a participant has progressed in accordance with RECIST 1.1.

Baseline radiological tumour assessments are to be performed no more than 28 days before the first dose/administration of study medication and ideally as close as possible to the start of study treatment. Tumour assessments are then performed every 8 weeks ( $\pm 1$  week) following start of study treatment up to 1 year, then every 12 weeks ( $\pm 1$  week) until objective disease progression.

If an unscheduled assessment is performed, and the participant has not progressed, every attempt should be made to perform the subsequent assessments at their scheduled visits. This schedule is to be followed in order to minimise any unintentional bias caused by some participants being assessed at a different frequency than other participants.

From the investigator’s review of the imaging scans, the RECIST 1.1 tumour response data will be used to determine each participant’s visit response according to RECIST version 1.1. At each visit, participants will be programmatically assigned a RECIST 1.1 visit response of CR, PR, SD or PD (see [Table 7](#)), using the information from target lesions (TLs), non-target lesions (NTLs) and new lesions and depending on the status of their disease compared with baseline and previous assessments. If a participant has had a tumour assessment which cannot be evaluated, then the participant will be assigned a visit response of not evaluable (NE) (unless there is evidence of progression in which case the response will be assigned as PD).

RECIST outcomes (i.e., PFS, ORR, etc.) will be calculated programmatically for the site investigator data from the overall visit responses.

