**4.9.6 Radiological progression.**

The analysis of radiological progression will be based on tumor assessments using RECIST 1.1 (soft tissue) and PCWG3 (bone) criteria.

Participants who have not progressed (i.e., who have a CR, PR, or SD by RECIST 1.1, and non-progressive for bone disease by PCWG3) at the time of analysis will be censored at the time of the latest date of their last evaluable RECIST assessment or bone scan assessment that showed fewer than 2 new lesions.

However, if the two or more consecutive scheduled radiological assessments immediately prior to progression or death were missing, the participant will be censored at the time of the latest evaluable RECIST 1.1 and bone scan assessment prior to the two or more missed assessments. (Note: NE visit is not considered as missed visit).

If the participant has no evaluable visits or does not have baseline data, he will be censored at Day 1 unless he dies within two visits of baseline (in which case the participant’s date of death will be used). The rPFS time will always be derived based on scan/assessment dates, not visit dates.

When the investigator is in doubt as to whether PD has occurred and therefore reassesses the participant at a later date, the date of the initial scan should be declared as the date of progression if the repeat scans confirm progression.

The requirements for determination and confirmation of radiographic progression by either bone scan (bone progression) or CT/MRI (soft tissue progression) are summarised in [Table 13](#).

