**4.9.9 Composite response**

Composite response will be defined on the basis of the following outcomes; if any of these occur in the absence of radiological or PSA progression (according to RECIST 1.1 for soft tissue and visceral

lesions, PCWG3 criteria for bone lesions, and PSA) participants will be considered to have responded:

- Investigator assessed radiological objective response by RECIST 1.1 for soft tissue and visceral lesions and PCWG3 criteria for bone lesions. Response must be confirmed at least 4 weeks later. Blinded Independent Central Review (BICR) assessment may be introduced if the cohort is expanded, subject to a protocol amendment.
- Conversion of CTC count from  $\geq 5/7.5\text{mL}$  blood (unfavourable) at baseline to  $< 5/7.5\text{mL}$  blood (favourable) (as per PCWG3 criteria) confirmed by a second consecutive value obtained 3 or more weeks later.
- PSA decline of  $\geq 50\%$  confirmed by a second consecutive measurement at least 3 weeks later (based on PCWG1 criteria).

For visits with non-evaluable radiological response, absence of radiological progression for that specific visit can be decided if there is any subsequent evaluable non progression response (CR/PR/SD). For visits with missing PSA assessment, absence of PSA progression for that specific visit can be decided if there is any subsequent non progressive PSA assessment available. Participants who discontinue study treatment without progression, receive a subsequent anti-cancer therapy and then respond will not be included as responders. More details on the derivation of composite response may be provided in in a separate programming guidance document if deemed necessary.

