#### 4.17.4 Radiological Objective Response Rate (Cohort B)

Radiological ORR is defined as the percentage of participants who have a confirmed investigator assessed response of CR or PR in their soft tissue disease assessed by RECIST 1.1 and bone scan status of non-PD or NE for their bone disease assessed by PCWG-3, and will be based on the molecularly eligible centrally confirmed evaluable for response set as well as evaluable for response set, and on a subset of participants with measurable disease in the molecularly eligible centrally confirmed evaluable for response set.

A confirmed response of CR/PR means that a response of CR/PR is recorded at 1 visit and confirmed by repeat imaging not less than 4 weeks after the visit when the response was first observed with no evidence of progression between the initial and CR/PR confirmation visit.

Data obtained up until progression, or last evaluable assessment in the absence of progression, will be included in the assessment of rORR. Participants who discontinue study treatment without progression, receive a subsequent anti-cancer therapy and then respond will not be included as responders in the rORR (i.e. both visits contributing to a response must be prior to subsequent therapy for the participant to be considered as a responder).

In the case where a participant has two non-consecutive visit responses of PR, then, as long as the time between the 2 visits of PR is greater than 4 weeks and there is no PD between the PR visits, the participant will be defined as a responder. Similarly, if a participant has visit responses of CR, NE, CR, then, as long as the time between the 2 visits of CR is greater than 4 weeks, then a best response of CR will be assigned.

The rORR will be based on the investigator RECIST data and using all scans regardless of whether they were scheduled or not.

Summaries will be produced that present the number and percentage of participants with a tumour response (CR/PR) based upon the number of participants with measurable disease at baseline per site investigator. A two-sided 80% confidence interval using Clopper-Pearson method will also be computed.

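### Table 11 codes a visit with non-evaluable soft tissue and no bone progression as PD and can never return NE

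*SAP*

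**What the plan says.** Section 4.9.5 derives the Cohort B overall radiological visit response from Table 11. The row at issue lists soft-tissue response, bone status, bone lesions present or absent, and the result: "NE Non-PD or NE Any PD".

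Other parts of the SAP treat a non-evaluable visit differently:

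- **4.9.1:** an assessment that cannot be evaluated is "assigned a visit response of not evaluable (NE) (unless there is evidence of progression in which case the response will be assigned as PD").
- **Table 9**, the corresponding row for target lesions, non-target lesions and new lesions: "NE Non-PD or NE or NA No (or NE) NE".
- **Table 12** derives the best overall radiological response from pairs of overall radiological responses. Three of its 11 rows take NE as an input: CR then NE, PR then NE, and NE then NE.
- **4.9.6:** "NE visit is not considered as missed visit". A participant with no evaluable visits is censored at Day 1 unless he dies within two visits of baseline.
- **4.9.9:** for a visit whose radiological response is non-evaluable, "absence of radiological progression for that specific visit can be decided if there is any subsequent evaluable non progression response (CR/PR/SD").
- **4.17.4:** a best response of CR is assigned "if a participant has visit responses of CR, NE, CR, then, as long as the time between the 2 visits of CR" exceeds 4 weeks. For two non-consecutive PRs more than 4 weeks apart, if "there is no PD between the PR visits, the participant will be defined as a responder".

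**The concern.** The row declares progression with no evidence of it. By its own inputs the bone component is either not progressing or not evaluable, and the soft tissue could not be read. Table 10 requires at least two new bone lesions plus confirmation before bone is PD, and neither bone status in this row meets that.

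Section 4.9.5 is the only place that defines the overall and best overall radiological response for Cohort B. Radiological ORR/BoR is a reported efficacy outcome in Table 6, and 4.16.2 lists the best overall radiological response among the composite components. The plan also uses data only up to progression for rORR (4.17.4) and for composite response (4.16.2). A false PD could therefore discard a later true response. Composite response is the Cohort B primary endpoint and the basis of the futility rule in 4.14.

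**Working it through.** The SAP states no figure to reproduce here, so the check is of the table's logic.

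**1. Outputs of Table 11.** The nine rows return, in order, CR, PR, PR, PR, SD, Non-PD, PD, PD, PD. NE is not among them.

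**2. All input combinations.** Six soft-tissue states (CR, PR, SD, NED, NE, PD) × three bone states (Non-PD, NE, PD) × two lesion states (present, absent) = 36. As written, the outputs are CR, PR, SD, Non-PD and PD only. All four combinations with soft tissue NE and bone Non-PD or NE return PD. Setting that row to NE changes exactly those four. Soft tissue NE with confirmed bone PD still returns PD through the last row.

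**3. Link to Table 12.** Its three NE rows need an input that Table 11 never produces, so 3 of 11 rows cannot be reached.

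**4. Effect on visit sequences.** Bone is Non-PD throughout, scans are 8 weeks apart, and data after PD are not used.

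| Soft-tissue sequence | Coded by Table 11 as written | Result as written | Result with the cell set to NE |
|---|---|---|---|
| NE, NE | PD, PD | PD | NE |
| PR, NE (no later response) | PR, PD | SD or PD | SD or NE |
| NE, PR, PR | PD, PR, PR | PD precedes the response | confirmed PR |
| PR, NE, PR | PR, PD, PR | PD precedes confirmation | confirmed PR under 4.17.4; SD or NE if Table 12 is read pairwise |
| PR, PR, NE | PR, PR, PD | confirmed PR | confirmed PR |

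The false PD harms classification when it comes before or between the two qualifying visits, or when there are only NE visits. After confirmation the best response is unaffected. PR then NE with nothing later is unconfirmed either way. The fourth row shows that correcting the cell is not enough if Table 12 is applied pair by pair.

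**5. Size of one lost responder, if endpoints are programmed from Table 11.**

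- Composite response, primary analysis (Table 1, n = 27): 1/27 = 3.7 points. With an assumed 6 responders, 6/27 = 22.2% (80% Clopper-Pearson CI 12.1 to 35.8) becomes 5/27 = 18.5% (9.3 to 31.7).
- Composite response, futility interim (4.14, minimum n = 12): 1/12 = 8.3 points. With an assumed 3 responders, 3/12 = 25.0% becomes 2/12 = 16.7%.
- rORR: the summary is "based upon the number of participants with measurable disease at baseline per site investigator". That subset has no stated size, because Table 4 also admits Cohort B participants on unfavourable CTC count alone. Assuming 14 to 27 such participants, the loss is 1/14 = 7.1 to 1/27 = 3.7 points.

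**The case against.** The strongest reply is that no endpoint section cites Table 11. Section 4.9.6 bases radiological progression on RECIST 1.1 and PCWG3 and refers to Table 13, under which a non-evaluable visit is not progression. Section 4.9.9 has its own rule for non-evaluable visits, and 4.17.4 defines rORR from soft-tissue response plus bone status. This largely stands for rPFS, which already has its own rule. For rORR and composite response it makes the effect conditional on the programming, not impossible. Section 4.17.4 works on visit responses, and for Cohort B the combined visit response is the one in Table 11.

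Two of the cross-references are weaker than the others. The note in 4.9.6 says only that NE is not a missed visit; the conflict with Table 11 comes from the Day 1 censoring rule and Table 13. The CR, NE, CR rule in 4.17.4 could refer to soft-tissue RECIST responses, where NE exists. On that reading rORR would count a responder whose best overall radiological response from 4.9.5 is not a response, so two reported results would disagree.

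The Table 11 footnote ties NE to a bone scan that was not performed. This does not rescue the row: its first column is the soft-tissue response, which Table 9 allows to be NE, and an unperformed scan is not evidence of progression.

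The cell may well be a clerical slip. It is still the stated derivation rule.

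**Conclusion.** The point holds. Table 11 is wrong as written and conflicts with 4.9.1, Table 9, Table 12, 4.9.6 and 4.9.9.

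- **Certain:** a wrong overall radiological visit response at every visit with non-evaluable soft tissue and no bone progression, three unreachable rows in Table 12, and a wrong best overall radiological response in the sequences identified above.
- **Conditional on programming from Table 11:** changes to rORR, composite response, CTC and PSA response (both assessed before radiological progression), duration of radiological response and rPFS. Each lost composite responder would cost 3.7 points at n = 27 and 8.3 points at n = 12.
- **Not computable:** the expected number of responders lost and the effect on the futility decision, since the SAP gives no NE rate and the threshold is redacted.

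The responder counts and the 14 to 27 range used above are assumptions. The finding would fall only if the signed SAP shows NE in that cell. It should be fixed before the analyses are run.

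**What to change.** 1. In Table 11, change the result for soft tissue NE with bone Non-PD or NE from PD to NE.
2. Add a sentence that radiological progression for all Cohort B endpoints follows 4.9.6 and Table 13.
3. Add a sentence that the 4.17.4 rules on confirmation across an intervening NE visit take precedence over a pairwise reading of Table 12. Otherwise PR, NE, PR stays unconfirmed even with the cell corrected.
4. Check the derivation programs against the corrected table before the interim and primary analyses.

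The cost is one table cell, two sentences and a programming check. No extra participants or data are needed.

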**Table 4: Analysis set**

Analysis set	Definition
Enrolled analysis set	All study participants who signed the informed consent form (including screening failures).
Evaluable for response set	Cohort A: All study participants with measurable baseline disease who received at least 1 dose of study intervention.  Cohort B: All study participants with measurable disease and/or unfavourable CTC count at baseline who received at least 1 dose of study intervention.
[a] Molecularly eligible centrally confirmed set	All molecularly eligible and centrally confirmed participants who received at least 1 dose of study intervention.

[a]Molecularly eligible centrally confirmed evaluable for response set
	
Cohort A: All molecularly eligible and centrally confirmed study participants with measurable baseline disease who received at least 1 dose of study intervention.
 
Cohort B: All molecularly eligible and centrally confirmed study participants with measurable disease and/or unfavourable CTC count at baseline who receive at least 1 dose of study intervention.

CCI [REDACTED]
	
CCI [REDACTED]

CCI [REDACTED]
	
CCI [REDACTED]

Safety set
	
All participants who received at least 1 dose of study intervention.

Interim analysis set
	
All participants in the molecular eligible centrally confirmed evaluable for response set with a chance to have at least two follow up RECIST assessments (i.e. all patients who received first dose of ceralasertib, at least 16 weeks prior to the data cut off date).

[a] Please refer to the latest CSP for more details regarding central confirmation. A separate specification document will be provided to support the programming of the ‘centrally confirmed’ flag.

Upon database release, protocol deviation and analysis set outputs will be produced and will be sent to AZ for review. Prior to database lock, analysis set classification meeting will be arranged to discuss the outputs and decide which participants and/or participant data will be excluded from certain analyses. Decisions made regarding the exclusion of participants and/or participant data from analyses will be made prior to database hard lock and will be documented and approved by AZ.

A summary on which analysis set will be used for each outcome variable is provided in [Table 5](#) (Cohort A) and [Table 6](#) (Cohort B).

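### Table 11 labels a Cohort B visit Non-PD when there is no soft-tissue disease and the bone scan was not done, so unknown bone status can pass as non-progression in the composite endpoint

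*SAP*

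**What the plan says.** Section 4.9.5, Table 11, contains the row "NED Non-PD or NE Any Non-PD" (soft tissue, bone status, bone lesions present or absent, overall result). Its footnote explains "NED = no evidence of disease (only relevant where there is no TL and NTL from baseline". For bone status NE, Table 10 says "Only relevant if a follow-up scan is not performed".

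Section 4.9.4 keeps the two assessments apart: "Bone lesions will be assessed by bone scan and will not be part of the RECIST v1.1 malignant soft tissue assessment".

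Section 4.9.9 counts a confirmed radiological response, CTC conversion or PSA decline as a composite response "if any of these occur in the absence of radiological or PSA progression". For visits with a non-evaluable radiological response it adds that "absence of radiological progression for that specific visit can be decided if there is any subsequent evaluable non progression response (CR/PR/SD").

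For the Cohort B primary analysis set, Table 4 requires central confirmation of molecular eligibility and otherwise takes in "study participants with measurable disease and/or unfavourable CTC count at baseline who receive at least 1 dose of study intervention". A participant with no soft-tissue lesions can therefore be in that set through the CTC criterion.

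**The concern.** A participant scored NED has no target or non-target lesion at baseline. Cohort B is metastatic, and the SAP follows metastases either in soft tissue and viscera or in bone, so the known disease is in bone. A soft-tissue result of NED says nothing about bone. When the bone scan is missing, the visit carries no information on the known disease, yet Table 11 returns Non-PD.

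These participants have no soft-tissue lesion that could show CR or PR. They can become composite responders only through CTC or PSA, and only without progression. Section 4.9.9 has a safeguard for unknown radiological status, but it is triggered by a non-evaluable visit, and a visit labelled Non-PD is not one. The direction is towards crediting a response. The endpoint is the Cohort B primary endpoint and also the basis of the futility guidance at the interim (section 4.14).

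**Working it through.** The plan gives no figure to reproduce here, so the check is first a reading of the tables and then a statement of scale.

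**Step 1. Table 11 for every soft-tissue result when the bone scan was not done (bone NE).**

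| Soft tissue | Overall result | Was any known baseline disease assessed? |
|---|---|---|
| CR | PR | Yes, soft tissue |
| PR | PR | Yes, soft tissue |
| SD | SD | Yes, soft tissue |
| NED | Non-PD | No |
| NE | PD | No |
| PD | PD | Yes, soft tissue, or a new lesion |

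The NED row is the only one that returns a non-progression result although no known baseline disease was assessed. NED with an actual non-progressing bone scan returns the same label.

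**Step 2. Comparison with Table 9.** With no target lesions (NA), non-target lesions NE and no new lesion, Table 9 gives NE. That is the same situation within soft tissue: the only disease being followed was not assessed. The two tables apply different principles.

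**Step 3. Passage into section 4.9.9.** No combination in Table 11 returns NE, because the soft-tissue NE row returns PD. A non-evaluable radiological visit, which the 4.9.9 safeguard needs as its trigger, therefore cannot arise from Table 11 as printed. For NED with bone NE the consequence is that the safeguard is not applied.

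**Step 4. What 4.9.9 accepts as clearance.** It lists CR, PR and SD. A participant in the NED row has Non-PD as the only non-progression result. If only Table 11 were changed to NE, a later clean bone scan would not literally satisfy 4.9.9.

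**Step 5. Effect per participant.** Cohort B plans about 27 participants, with at least 12 at the interim.
- 1/27 = 3.7 points; 1/12 = 8.3 points.
- Illustration with assumed counts and the planned 80% Clopper-Pearson interval: 6/27 = 22.2% (12.1 to 35.8) against 5/27 = 18.5% (9.3 to 31.7); 3/12 = 25.0% (9.6 to 47.5) against 2/12 = 16.7% (4.5 to 38.6).

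**Step 6. Likely number affected.** All inputs other than 27 and the scan weeks are assumptions.
- Participants with no soft-tissue disease: 20% to 40% of 27, about 5 to 11.
- Scans at weeks 8, 16 and 24, of which 5% to 10% are missed: 5 × 3 × 0.05 = 0.75 to 11 × 3 × 0.10 = 3.3 mislabelled visits.
- For a false credit, bone progression must also be present at that visit (assume 10% to 20%) and a CTC or PSA response must depend on it (assume 20% to 30%). Treated as independent: 0.75 × 0.10 × 0.20 = 0.015 to 3.3 × 0.20 × 0.30 = 0.198 participants.
- As a share of 27: 0.015/27 = 0.06 points to 0.198/27 = 0.7 points.

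Independence is a simplification. Scans missed because the participant is deteriorating would raise the figure; a negative association between bone progression and CTC or PSA response would lower it.

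**The case against.** The strongest case against is that the link to the primary endpoint is inferred and the effect small.

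- Section 4.9.9 defines progression by RECIST 1.1, PCWG3 and PSA criteria and does not cite Table 11. It also says that a separate programming guidance document may give more detail, and that document is not at hand. This stands as a limit. Table 11 is nevertheless the only rule in the SAP for combining soft tissue and bone at a visit, and an optional document does not correct an explicit row.
- The visit is not wholly unassessed. A new soft-tissue lesion still gives PD, and PSA progression is a separate condition. Both stand; the gap is confined to bone.
- A reader might infer that skipping a bone scan automatically secures a response. The SAP does not support that. Bone progression needs a confirmatory scan at least 6 weeks later, unconfirmed new lesions are Non-PD in any case (Table 10), and later scans are still compared with baseline or with the first post-baseline scan. A missed scan usually delays the finding of bone progression rather than erasing it.
- A reader might also take the 0.75 to 3.3 mislabelled visits as that many false responders. They are not: several further conditions must hold at the same visit.
- Section 4.6.2 lists persistently missing efficacy assessments among the deviations and allows a sensitivity analysis if more than 10% of a cohort has significant deviations affecting the primary endpoint. This helps with repeated omissions, not with one missed scan.

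**Conclusion.** The inconsistency is real. Table 11 gives non-progression to a visit at which the only known disease site was not imaged, contrary to the principle in Table 9. If Table 11 feeds section 4.9.9, the check for non-evaluable visits is bypassed and a CTC or PSA response can be credited with bone status unknown.

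The size is 3.7 points per wrongly credited participant at n=27 and 8.3 points at n=12. The SAP does not say how many would be affected; on the assumptions above the expected number is well below one. The documents do not support a claim that the composite rate is materially inflated. The case for acting is that the rule is explicit, errs towards response in a small cohort and is cheap to correct.

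**What to change.** Make two edits together.

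1. In Table 11, split the NED row: NED with bone Non-PD gives Non-PD; NED with bone NE gives NE.
2. In section 4.9.9, add Non-PD to the CR, PR and SD responses that can clear a non-evaluable visit, so that a later evaluable, non-progressing bone scan is sufficient.

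The first edit without the second would bias the other way: a true CTC or PSA responder with one missed scan could never be cleared on a literal reading. It would also help to state in 4.9.9 that Table 11 supplies the radiological status, and to review the adjacent row (soft tissue NE giving PD) at the same time, since it treats missing assessment in the opposite direction. Correcting that row alone does not resolve this point.

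The cost is one table row, one list entry and their programming. The downside is that a response at such a visit counts only once a later evaluable scan is available, so a participant with no later scan would not be credited on the strength of that visit.
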